6.2.4 Unexpected Adverse Drug Reaction

An “unexpected” adverse drug reaction is an adverse reaction, the nature or severity of which is not consistent with the applicable product information (e.g., Investigator’s Brochure for drugs that are not yet approved and Product Information for approved drugs, respectively) [\[ICH E2A, 1995\]](#).

6.2.5 Suspected Unexpected Serious Adverse Reactions

The Sponsor evaluates any SAE that has been reported regarding seriousness, causality and expectedness. If the event is related to the IMP and is both serious and unexpected, it is classified as a suspected unexpected serious adverse reaction (SUSAR).

6.2.6 Assessment of Severity

The Investigator is required to grade the severity or toxicity of each AE.

Investigators will reference the National Cancer Institute – Common Terminology Criteria for Adverse Events ([NCI-CTCAE, 2017](#)), version 5.0 (publication date: 27 November 2017), a descriptive terminology that can be used for AE reporting.

A general grading (severity/intensity; hereafter referred to as severity) scale is provided at the beginning of the above referenced document, and specific event grades are also provided.

If a particular AE's severity is not specifically graded by the guidance document, the Investigator is to use the general [NCI-CTCAE](#) definitions of Grade 1 through Grade 5 following his or her best medical judgment.

The five general grades are:

- Grade 1 or Mild
- Grade 2 or Moderate
- Grade 3 or Severe
- Grade 4 or Life-threatening
- Grade 5 or Death

6.3 Reporting of Serious Adverse Events and Other Safety Related Events

6.3.1 Reporting of AEs

All AEs must be reported to the CRO and/or Sponsor through the eCRF and within the data entry timeline defined for this trial and stipulated in the site agreement.

6.3.2 Reporting of SAEs

All SAEs must be reported immediately and within a maximum of 24 hours to the CRO and/or Sponsor of the trial through the eCRF.

The CRO/Sponsor will re-evaluate the SAE and queries will be raised in the eCRF and returned to the site, requesting clarification or follow-up information if needed. After the initial SAE report, the Investigator is required, proactively, to provide further information regarding the subject's condition. All follow-up information for other SAEs must be entered into the CRF as soon as possible, within 24 hours after it becomes available. In case e-CRF access is not possible, the Investigator must send an email with the respective filled out paper forms to: [contact]. Local fax-numbers will be made available in the Investigator Site File, should email not work either.

Serious AEs resulting in death will be reported to the Ethics Committee within 7 days.

The minimum data required for a report is:

- Subject ID
- Trial code/protocol number
- Date of enrolment
- Date and time of start of SAE
- Description of SAE
- Severity of SAE
- Assessment of causality relationship to IMP
- Name and contact details of person reporting the event

6.3.3 Reporting of SUSARs

A SUSAR for an event that is life-threatening or fatal, needs to be reported to the IEC and competent authorities (CAs) within 7 calendar days,

All other SUSARs need to be reported to the IEC and CAs within 15 calendar days.

As necessary, the Sponsor must inform all Investigators, IEC and CAs participating in the clinical trial of the occurrence of a SUSAR.

6.3.4 Reporting of Safety Signals

All suspected new risks and relevant new aspects of known adverse reactions that require safety-related measures, i.e., so-called safety signals, must be reported to the Sponsor within 24 hours. The Sponsor must report the safety signals within 7 days to the IEC and CAs.

The Sponsor must immediately inform all participating Investigators about all safety signals. The other IECs and CAs involved in the trial will be informed about safety signals by the Sponsor as necessary.

6.3.5 Reporting and Handling of Pregnancies

Pregnant subjects must immediately be withdrawn from the clinical trial. Any pregnancy during the treatment phase of the trial and within 90 days after discontinuation of trial medication will be reported to the Sponsor within 24 hours.

The course and endpoint of the pregnancy should be followed up carefully, and any abnormal endpoint regarding the mother or the child should be documented and reported.

A female subject must be instructed to stop taking the IMP and immediately inform the Investigator if she becomes pregnant. Pregnancies occurring in female partners of male subjects must also be reported immediately to the Investigator. Pregnancies occurring in female subjects or female partners of male subjects up to 90 days after the completion of dosing must also be reported to the Investigator.

If the Investigator becomes aware of a pregnancy occurring in the subject and/or partner of a subject participating in the trial, it should be reported to the Sponsor. The subject and/or partner should be counseled and followed as described below.

The Investigator should report all pregnancies to the Sponsor within 24 hours of becoming aware of them. The pregnancy report for a female partner of the male subject must be forwarded within 24 hours after written consent is obtained from the pregnant partner. The Investigator will make arrangements for the subject and/or partner to be seen by a specialist who can discuss any risks of continuing with the pregnancy. Monitoring of the subject and the child should continue until 4 weeks after the outcome of the pregnancy is known.

6.3.6 Periodic Reporting of Safety

An annual safety report will be submitted once a year to the local IEC via the local Investigator and to CAs via the Sponsor or Contract Research Organization.

6.4 Follow up of Serious Adverse Events

Serious AEs should be followed until resolution or stabilization. Subjects with ongoing SAEs at trial termination (including safety visit) will be followed up until recovery, return to baseline status or stabilization. If after follow-up, return to baseline status or

stabilization cannot be established, an explanation should be recorded on the eCRF SAE form.

6.5 Abnormal Laboratory Findings and Other Abnormal Investigational Findings

Abnormal laboratory findings and other abnormal investigational findings (e.g., on an ECG trace) should not be reported as AEs unless they are associated with clinical signs and symptoms, lead to treatment discontinuation or are considered otherwise medically significant by the Investigator. If a laboratory abnormality fulfills these criteria, the identified medical condition must be reported as the AE rather than the abnormal value itself.

Elevations (or new elevations from baseline) in transaminases or tests of liver function will be closely monitored. Laboratory tests (AST, ALT, alkaline phosphatase, GGT, total bilirubin, viral serologies) will be used to depart other causes of liver injury from drug-induced liver injury. Subjects with persistent or new deterioration of hepatic function will be followed-up.

6.6 Trial Specific Safety Considerations

6.6.1 Considerations on IMP dose reduction and temporary discontinuation of IMP

If the Investigator reduces the IMP dose due to safety reasons, documentation as an AE is required.

If the Investigator reduces or temporarily discontinues IMP, resumption of IMP or return to the prescribed dose must be based on the medical condition of the subject and the Investigator's clinical judgment.

Reduction of IMP can be from 5.0 mg to 2.5 mg or from 2.5 mg to 0 mg. No other dose adjustments are allowed. The Investigator should attempt to return to the per protocol dose as soon as the medical condition of the subject allows. If the subject does not continue to tolerate the per protocol dose the Investigator may choose to resume IMP administration at the lower dose of 2.5 mg weekly.

There is no limit to the number of dose reductions for an individual subject during the trial. However, the Investigator should discuss with the subject and use their clinical judgment to determine if it is safe and appropriate for the subject to continue, if numerous IMP discontinuations and/or reductions have been required.

Changes and discontinuations must be discussed with the Medical Monitor. If the subject's medical condition allows, this discussion may occur prior to changes but may occur afterwards if this is not possible (e.g., an AE necessitating an immediate halt). The final decision to reduce or discontinue IMP will be that of the Investigator.

Dose changes and the rationale will be documented in the medical records, in the subject diary (for IMP administration at the subject's home) and in the eCRF. Missed doses will not be made up for, i.e., the treatment period will not be prolonged due to temporary discontinuation. Reporting as a protocol deviation is required.

6.6.2 Individual Subject Stopping Rules

During the trial, liver toxicity will be monitored according to guidelines from the US Food and Drug Administration (FDA) (FDA Guidance for Industry: Drug-Induced Liver

Injury: Premarketing Clinical Evaluation, 2009) and treatment will be discontinued if any of the following stopping criteria are met for subjects with ALT and AST <1.5 ULN at baseline:

- Alanine aminotransferase or AST >8 × ULN once
- Alanine aminotransferase or AST >5 × ULN for more than 2 weeks
- Alanine aminotransferase or AST >3 × ULN and total bilirubin >2 × ULN or INR >1.5 for a person not using anticoagulant drug and INR >3 for a person on anticoagulant therapy such as warfarin.
- Alanine aminotransferase or AST >3 × ULN and clinical signs of fatigue, nausea, vomiting, right upper quadrant pain or tenderness, fever, rash, and/or eosinophilia

Patients with SBS-IF, who are dependent on PN, commonly develop abnormal liver function tests. This condition is known as intestinal failure-associated liver disease or PN-associated liver disease [Abu-Wasel, 2014]. In this case, ALT and or AST levels may be elevated at baseline; therefore, the stopping rules for these subjects have been adapted based on published guidelines [Treem, 2021]. For subjects with baseline AST and/or ALT values \geq 1.5 ULN, treatment will be discontinued if any of the following stopping criteria are met:

- Alanine aminotransferase or AST \geq 2 x baseline or 5 x ULN (whichever comes first) **AND** total bilirubin (TBL) \geq ULN (if normal at baseline) or TBL \geq 1.5 x baseline (if elevated at baseline)
- Alanine aminotransferase or AST \geq 2 x baseline or 5 x ULN (whichever comes first) **AND** INR \geq 1.5
- Alanine aminotransferase or AST \geq 3 x baseline or 8 x ULN (whichever comes first)
- Alkaline phosphatase \geq 2 x baseline and direct bilirubin 1 mg/dL (17.1 mol/L) over baseline

The IMP should not be restarted until a diagnostic evaluation is completed. A re-challenge may be considered in case of IMP discontinuation due to meeting one of the above stopping criteria after a consultation and approval by the Medical Monitor. Additional visits to the site for un-scheduled laboratory samplings should be arranged in such a case, or the subject should see their local doctor for laboratory assessments as agreed with the Investigator. In case of abnormal laboratory results of CTCAE Grade 3 or higher as assessed by the subject's local doctor, a re-assessment should be scheduled at the site. All results will be filed in the medical chart, assessed by the Investigator, and entered in the eCRF accordingly.

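### In Protocol 6.6.2 the baseline-multiple liver stopping limits for subjects with one raised transaminase also bind the enzyme that was normal, so a mandatory stop can fall at a low or even normal value of that enzyme

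*Protocol*

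**What the plan says.** Protocol 6.6.2 assigns each subject to one of two lists by baseline transaminases.

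**First list.** Treatment stops if any of the "stopping criteria are met for subjects with ALT and AST <1.5 ULN at baseline". On a transaminase alone the limits are "Alanine aminotransferase or AST >8 × ULN once" and "Alanine aminotransferase or AST >5 × ULN for more than 2 weeks". The lowest transaminase level named anywhere in this list is above 3 x ULN, and there it is paired with a bilirubin/INR condition or with clinical findings ("Alanine aminotransferase or AST >3 × ULN and clinical signs of fatigue, nausea, vomiting" and others).

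**Second list.** It opens "For subjects with baseline AST and/or ALT values" at or above 1.5 x ULN. The reason given is that "ALT and or AST levels may be elevated at baseline; therefore, the stopping rules for these subjects have been adapted", with a published guideline cited. Its criteria name ALT or AST without saying which is meant when only one was raised:

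- at or above "2 x baseline or 5 x ULN (whichever comes first"), together with either a total bilirubin condition (reaching ULN if normal at baseline, or 1.5 x baseline if elevated) or an INR of at least 1.5;
- at or above "3 x baseline or 8 x ULN (whichever comes first"), with no further condition.

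A further criterion uses alkaline phosphatase with direct bilirubin and is not at issue here. In both lists the stop is mandatory once any criterion is met. The SAP does not restate or qualify the rule.

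**The concern.** Assignment to the second list is by subject, but its limits apply by enzyme. A subject enters because one enzyme is raised, and the multiple of baseline then also attaches to the other enzyme, whose baseline may be well within normal. A multiple of a low number is a low number. No minimum in units of ULN is set, and the lower of the two limits governs.

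Such subjects can be enrolled. Exclusion criterion 15 rules out ALT or AST above 5 x ULN, and above 3 x ULN only with bilirubin, INR or clinical findings. Section 6.6.2 itself says abnormal liver tests are common in this population.

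What is at stake is limited but real in a trial of this size:

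- A stop interrupts dosing until a diagnostic evaluation is complete and the Medical Monitor has approved a restart.
- Doses missed through temporary discontinuation are not made up (6.6.1). SAP 9.7.4 excludes subjects from the sensitivity analyses at 1 missed injection by Week 4, 5 by Week 24 and 10 by Week 48.
- Treatment discontinuations are tabulated with the safety results, which are the primary endpoints.
- One site may read the multiple as applying only to the raised enzyme and another may follow the text, so identical laboratory values could be handled differently.

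**Working it through.** **Inputs from Protocol 6.6.2**

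- Entry to the second list: AST and/or ALT at or above 1.5 x ULN at baseline.
- Second list, enzyme alone: lower of 3 x baseline and 8 x ULN.
- Second list, enzyme with bilirubin or INR condition: lower of 2 x baseline and 5 x ULN.
- First list, enzyme alone: above 8 x ULN once, or above 5 x ULN for more than 2 weeks.
- First list, lowest level with a further condition: above 3 x ULN.

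**Assumption.** The documents give no baseline enzyme values. Let b be the baseline of the non-raised enzyme in units of ULN, taken over 0.3 to 1.0.

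**Formulas.** Limit alone = min(3b, 8). Limit with bilirubin or INR = min(2b, 5).

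| b (x ULN) | Alone, min(3b, 8) | With bilirubin or INR, min(2b, 5) |
|---|---|---|
| 0.3 | 0.9 | 0.6 |
| 0.4 | 1.2 | 0.8 |
| 0.5 | 1.5 | 1.0 |
| 0.75 | 2.25 | 1.5 |
| 1.0 | 3.0 | 2.0 |

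**When the limit falls in the normal range.** 3b ≤ 1 when b ≤ 1/3 = 0.33. 2b ≤ 1 when b ≤ 1/2 = 0.50.

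**Whether the ULN cap helps.** 3b is below 8 whenever b < 8/3 = 2.67, and 2b is below 5 whenever b < 5/2 = 2.5. For a normal enzyme (b ≤ 1) the multiple of baseline always governs.

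**Comparison with the first list.** For b ≤ 1 the stand-alone limit is at most 3 x 1.0 = 3.0 x ULN. Every transaminase criterion in the first list requires more than 3 x ULN, so a value at any limit in the table meets none of them.

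**Worked case.** Baseline AST 1.6 and ALT 0.3 x ULN; later AST 1.6 and ALT 0.9 x ULN.

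- The subject is on the second list because 1.6 ≥ 1.5.
- AST: min(3 x 1.6, 8) = 4.8, and 1.6 does not reach it.
- ALT: min(3 x 0.3, 8) = 0.9, and 0.9 reaches it, so treatment must stop on an ALT within the normal range.
- If the multiple applied only to the raised enzyme, nothing would be met.
- In a subject with both enzymes below 1.5 x ULN at baseline, an ALT of 0.9 x ULN meets no stopping criterion.

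**Frequency.** The documents state neither how many subjects have exactly one raised enzyme nor the within-subject variability of ALT or AST. The chance of a stop cannot be calculated from them.

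**The case against.** **The two lists are meant to differ.** They cover separate groups, so different actions are no contradiction in themselves. The second list is also stricter for an enzyme that was raised: at baselines of 1.5 and 2.0 x ULN the stand-alone limits are 3 x 1.5 = 4.5 and 3 x 2.0 = 6.0 x ULN, against above 8 x ULN in the first list, and this holds up to 2.67 x ULN. Closer control of subjects with existing liver abnormality may be intended, and the text cites a guideline that cannot be checked from these documents. This stands: a reader might infer that strictness shows an error, and it does not. What remains is narrower. The only reason stated is elevation at baseline, and that does not explain a multiple-of-baseline limit on an enzyme that was not elevated.

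**2 x baseline does not stop treatment alone.** Correct; the bilirubin or INR condition must also be met. The INR contrast is weak as well, because the first list leaves unclear whether INR needs bilirubin beside it.

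**Other subjects are not left without action.** Also correct. Section 6.5 requires close monitoring of transaminase elevations, including new ones from baseline. The contrast concerns stopping criteria only.

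**A stop does not mean lost data.** A reader might infer that these subjects drop out of the efficacy analysis, the more so as 2.2.2 speaks of discontinuing from the trial those who meet a stopping rule. But 6.6.2 allows re-challenge with Medical Monitor approval, 3.5 asks subjects who stop treatment to continue assessments to Week 52, and the efficacy analyses use observed values in the Full Analysis Set. Loss is possible but not automatic.

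**Conclusion.** The point holds as a fault in the wording of 6.6.2. Followed literally, the second list forces a stop on a non-raised enzyme at 0.9 to 3.0 x ULN for assumed baselines of 0.3 to 1.0 x ULN. The limit lies inside the normal range at or below 0.33 x ULN, and at or below 1.5 x ULN for baselines up to 0.5 x ULN. The arithmetic is exact given the baseline; only the baselines are assumed.

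Its effect on the trial is unknown. SAP Section 2 reports 9 subjects enrolled, so one affected subject would be 1/9 = 11%, but the number with exactly one raised enzyme is not given and may be zero. The documents do not support a claim that such stops are frequent, that the limits for raised enzymes are wrong, or that any particular limit should replace the present ones.

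**What to change.** Reconcile three parts of 6.6.2: the sentence defining who falls under the second list, the stated purpose of that list, and its ALT/AST criteria. State to which enzyme each baseline multiple applies when only one of ALT and AST is raised at baseline. If applying it to both is intended, say so and give the reason. The limits themselves are for the sponsor's hepatic-safety adviser, and none is suggested here.

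No SAP change is needed. Sections 9.8.2 and 9.8.3 already list adverse events leading to permanent discontinuation and all chemistry results by subject, so with 9 subjects the triggering value and its baseline can be read directly.

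The text change is about one sentence and needs no extra tests. It does alter a safety stopping rule, so it would need ethics committee and authority approval. SAP Section 2 says the French site remains on protocol version 3 after version 4 was rejected there, so the clarification would have to be handled for both versions.

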6.6.3 Trial stopping criteria

The following trial stopping rules are based on the AE criteria of the [NCI-CTCAE](#), 2017 version 5.0, related to ALT, AST, GGT, alkaline phosphatase, and TBL elevations.

Enrollment of new subjects should be interrupted should two or more subjects experience CTCAE Grade 3 events, or one or more subjects experience CTCAE Grade 4 events not clearly related to the underlying disease. Trial enrollment may be resumed following the review of all available safety data, if the totality of the data suggests that the event is unlikely to be related to the trial treatment. The trial may be

TMP no.: TMP-CD-04_1
Version no.: 1.0
Effective date: 10-Oct-2019

Phase II Study of Apraglutide in SBS

terminated if, following the review of the safety data, it has not been possible to demonstrate that the AE has a clear relationship to the underlying disease or associated co-morbidity (and not to IMP administration).

7. DATA ANALYSIS AND STATISTICAL CONSIDERATIONS

7.1 General Considerations

The statistical evaluation of the trial will include descriptive statistics of the primary and secondary endpoints reflecting the exploratory nature of the trial. In addition, simple analyses will be provided for the efficacy endpoints and patient reported outcomes.

7.1.1 Primary Endpoints

- Adverse events (system organ class, frequency and severity)
- Adverse events of special interest:
 - Injection site reaction
 - Gastrointestinal obstruction
 - Gallbladder, biliary and pancreatic disease
 - Fluid overload
 - Colorectal polyps
 - Malignancies
- Clinical chemistry, hematology, hemostasis, ADAs, and urine analysis

7.1.2 Secondary Endpoints

Efficacy endpoints related to PS volume

- Relative change from baseline in actual weekly PS volume at Weeks 24 and 52
- Absolute change from baseline in actual weekly PS volume at Weeks 24 and 52
- Subjects who achieve a reduction of at least 1 day per week of PS from baseline at Weeks 24 and 52
- Clinical responders (20% reduction of PS volume from baseline) at Weeks 24 and 48
- Subjects reaching enteral autonomy at Weeks 24 and 52
- Energy reduction in the PN from baseline at Weeks 24 and 52

Efficacy endpoint related to nutritional, fluid (wet weight), and electrolyte absorption

- Change in absolute absorption of energy, over metabolic balance periods from baseline to Week 48
- Relative change in absorption of energy over metabolic balance periods from baseline at Week 48
- Change in absorption of macronutrients over metabolic balance periods from baseline at Week 48
- Change in absolute absorption of energy over metabolic balance periods from baseline at Week 4
- Change in absorption of macronutrients over metabolic balance periods from baseline at Week 4

- Changes in urine output and urinary electrolytes (sodium, potassium, calcium, and magnesium) over metabolic balance periods from baseline at Week 4 and at Week 48

Patient reported outcomes

- [REDACTED]
- Patient Global Impression of Change at Week 24 and 52
- Changes from baseline in PGI-TS at Weeks 24 and 52
- Changes from baseline in PGI-SPS at Weeks 24 and 52
- Changes from baseline in PGI-PSI at Weeks 24 and 52

Pharmacokinetic/Pharmacodynamic related endpoints

- Trough plasma concentration
- Plasma citrulline levels

7.1.3 Exploratory Endpoints

Endpoints related to nutritional status

- Changes from baseline in lean body mass, bone mineral content, and fat mass by DEXA scan from baseline at Weeks 4, 24, and 48
- Change in body weight from baseline at Weeks 4, 24 and 52
- Change in dietary intake of wet weight, energy, macronutrients, fluid, and electrolytes (sodium, potassium, calcium, and magnesium) from baseline at Week 4 and 48
- Change in fecal excretion of wet weight, energy, macronutrients, fluid, and electrolytes (sodium, potassium, calcium, and magnesium) from baseline at Week 4 and 48

Endpoints related to efficacy

- Change from baseline in the total time per day that subjects infuse PS at Weeks 24 and 52
- Change from baseline in the total time per week that subjects infuse PS at Weeks 24 and 52
- Change in electrolytes, minerals, macronutrients, and other contents of the PS from baseline at Weeks 24 and 52

Patient reported outcomes

- Short Bowel Syndrome with Intestinal Failure and Colon-in-Continuity - Changes from baseline in Quality of Life Questionnaire at Weeks 24 and 52
- Short Bowel Syndrome with Intestinal Failure - Changes from baseline in Treatment Impacts - Quality of Life Questionnaire at Weeks 24 and 52

[REDACTED]

[REDACTED]

[REDACTED]

[REDACTED]

- [REDACTED]
- [REDACTED]
- [REDACTED]
- [REDACTED]
- [REDACTED]
- [REDACTED]
- [REDACTED]
- [REDACTED]

